5.2 Secondary Outcomes

- Time to recovery, defined as time to reaching level 5, 6, or 7 on the COVID Outcomes Scale, which is the time to the earlier of final liberation from supplemental oxygen or hospital discharge
- All-location, all-cause 14-day mortality (assessed on Study Day 15)
- All-location, all-cause 28-day mortality (assessed on Study Day 29)
- COVID Ordinal Outcomes Scale on Study Day 3
- COVID Ordinal Outcomes Scale on Study Day 8
- COVID Ordinal Outcomes Scale on Study Day 29
- Composite of death or receipt of ECMO through Day 28
- Oxygen-free days through Day 28
- Ventilator-free days through Day 28
- Vasopressor-free days through Day 28
- ICU-free days through Day 28
- Hospital-free days through Day 28

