7.5 Analysis of Secondary and Safety Outcomes

Ordinal secondary will be analyzed using a proportional odds model with randomized group assignment as an independent variable and the covariables used in the primary model. Binary secondary outcomes will be analyzed using multivariable logistic regression models with the same pre-specified covariates. Survival and hospital discharge through day 28 will be analyzed using multivariable proportional hazards regression with the same covariates in the primary outcome model. For the hospital discharge model, death will be treated as a competing risk, and the sub-distribution hazard ratio will be reported.⁶ Safety outcomes will be analyzed with simple logistic regression without co-variable adjustment.

Detailed data on receipt of invasive mechanical ventilation, vasopressors, intensive care unit admission, and hospitalization were collected during the index hospitalization, but not after discharge from the index hospitalization. Therefore, the main analysis of the associated “-free day” outcomes will use information regarding receipt of the supportive therapy between randomization and hospital discharge or Study Day 29, whichever occurs first (“in-hospital outcome”). Information on death between discharge from the index hospitalization and Study Day 29 is systematically available via follow-up phone calls. Hence, we will use all-cause, all-location death in the calculation of “-free day” outcomes.

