Death between randomization and 14 days after randomization from any cause and in any location, including after discharge from the index hospitalization. Data on death were collected from the electronic health record during the hospitalization and then from telephone calls to the patient or surrogate after discharge on Study Day 8, 15 and 29.

All-location, all-cause 28-day mortality

Death between randomization and 28 days after randomization from any cause and in any location, including after discharge from the index hospitalization. Data on death were collected from the electronic health record during the hospitalization and then from telephone calls to the patient or surrogate after discharge on Study Day 8, 15 and 29.

Survival through 28 days

Dead versus survived will be recorded between randomization and 28 days following randomization using in-hospital data and follow-up calls post-discharge on Study Day 8, 15, and 29. Using these data, survival curves through 28 days following randomization will be constructed.

Hospital discharge through 28 days

Time of hospital discharge from the index hospitalization for COVID-19 will be recorded. Using these data, time to hospital discharge curves through 28 days following randomization will be constructed. Death will be treated as a competing risk.

COVID Ordinal Outcomes Scale on Study Day 3

Clinical status 2 days after randomization (measured on Study Day 3) as assessed with the seven-category COVID Ordinal Outcome Scale, as described in the section on the *Primary Outcome*. Data on clinical status were collected from the electronic health record during the hospitalization. Patients discharge prior to Study Day 3 will have the Day 3 COVID Ordinal Outcome Scale coded as level 6 (not hospitalized with limitation in activity).

COVID Ordinal Outcomes Scale on Study Day 8

Clinical status 7 days after randomization (measured on Study Day 8) as assessed with the seven-category COVID Ordinal Outcome Scale, as described in the section on the *Primary Outcome*. Data on clinical status were collected from the electronic health record during the hospitalization and then from telephone calls to the patient or surrogate after discharge from the index hospitalization (“all-location outcome”).

COVID Ordinal Outcomes Scale on Study Day 29

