Clinical status 28 days after randomization (measured on Study Day 29) as assessed with the seven-category COVID Ordinal Outcome Scale, as described in the section on the *Primary Outcome*. Data on clinical status were collected from the electronic health record during the hospitalization and then from telephone calls to the patient or surrogate after discharge from the index hospitalization (“all-location outcome”). Missing data for the COVID Ordinal Outcomes Scale on Day 29 will be handled in the same fashion as describe for the primary outcome.

Composite of death or receipt of ECMO through Day 28

Death or receipt of extra-corporeal membrane oxygenation (ECMO) between randomization and discharge from the index hospitalization or 28 days after randomization, whichever occurs first (“in-hospital outcome”). Patients who were receiving ECMO at the time of randomization could qualify for this outcome by experiencing death, but not by continuing to receive ECMO.

Days Free of Support

For all outcomes related to days alive and free from a supportive therapy, “-free days” were calculated as the number of whole calendar days from 00:00 on the day of randomization (Study Day 1) to 23:59 on Study Day 28. The day of randomization contributed to the count of “-free days”. Days between randomization and the first receipt of the supportive therapy and days following the last day of the support therapy both counted toward the total number of “-free days”. Days alive and free of the supportive therapy that occurred between periods receiving support did not count toward “-free days”.

Information on organ support therapies (oxygen, ventilation, vasopressors, ICU care) were collected during the index hospitalization (“in-hospital data”) while death was collected both in-hospital and out-of-hospital to Study Day 29 (“all-location data”). Thus, patients who died at any time before Study Day 29 were coded as having zero-free days.

Oxygen-free days through Day 28

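### The SAP's death-or-ECMO composite stops counting deaths at index discharge, although it is named as an outcome through Day 28 and the later deaths are collected

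*SAP*

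**What the plan says.** Protocol 5.2 and SAP 6.2 both list the outcome as "Composite of death or receipt of ECMO through Day 28". Neither list adds a discharge limit, and the protocol defines the outcome no further. SAP Appendix A treats it as binary and analyses it by covariate-adjusted logistic regression.

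The working definition is in SAP Appendix B. It counts death or receipt of ECMO "between randomization and discharge from the index hospitalization or 28 days after randomization, whichever occurs first" and labels the whole entry an in-hospital outcome. A patient already on ECMO at randomisation can qualify only by dying.

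Elsewhere the SAP treats death differently:

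- SAP 7.5 explains that detailed organ-support data stop at index discharge, but adds: "Information on death between discharge from the index hospitalization and Study Day 29 is systematically available via follow-up phone calls". It continues "Hence, we will use all-cause, all-location death in the calculation of" the days-free outcomes.
- Appendix B, on days free of support, repeats the rule: "Thus, patients who died at any time before Study Day 29 were coded as having zero-free days".
- Appendix B defines 28-day mortality as "Death between randomization and 28 days after randomization from any cause and in any location, including after discharge from the index hospitalization".

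**The concern.** The name promises every death through Day 28, but the definition drops any death after index discharge. The SAP's reason for in-hospital limits is that organ support was not recorded in detail after discharge. That can justify limiting ECMO. It cannot justify limiting death, which is followed by telephone to Study Day 29 in all patients.

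Two consequences follow. First, an outcome that means death or something else by Day 28 should never have fewer events than death by Day 28. Under this definition it can, and both results would be reported over the same nominal period. Second, discharge happens after randomisation and treatment could affect its timing. If treatment moves deaths from before discharge to after it, the composite registers a benefit that is not there.

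**Working it through.** **Side by side.** The documents state no event rate or power for this composite, so there is no planned figure to reproduce. The check is to follow one patient through the SAP's definitions. The patient is discharged on Day 5, dies on Day 10 and never receives ECMO.

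| Outcome | How the death is handled |
|---|---|
| 28-day mortality | Counted |
| Survival through 28 days | Counted |
| Ordinal scale, Day 29 | Level 1 |
| Days-free outcomes | Score 0 |
| Death or ECMO through Day 28 | Event-free |

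The in-hospital label does not settle how death is handled, because the oxygen, ventilator, vasopressor and ICU entries carry it too. Those entries add an explicit rule that death before Study Day 29 scores zero. The composite entry has no such rule.

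**When the composite falls below mortality.** In one arm let *p* be 28-day mortality, *s* the share of those deaths that follow discharge, and *e* the proportion who count through ECMO and do not die before discharge or Day 28. Then

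composite = *p*(1 − *s*) + *e*,

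which is below *p* whenever *e* < *p s*.

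**Inputs.**

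- Enrolment of 510 (SAP 4.3).
- *p* from 0.115 (Day 15 mortality in the network's earlier vitamin D trial, Protocol 7.1) to 0.17 (upper in-hospital mortality in case series, Protocol 2.1.3). Neither is a 28-day figure for this population; using them as *p* is an assumption.
- *s* and *e* are not in the documents. All values below are assumptions.

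**Events lost** (510 × *p* × *s*), which is also the break-even number of ECMO recipients:

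- *p* = 0.115: 510 × 0.115 × 0.05 = 2.9; 510 × 0.115 × 0.10 = 5.9.
- *p* = 0.17: 510 × 0.17 × 0.05 = 4.3; 510 × 0.17 × 0.10 = 8.7.

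A second route gives a similar range. If 60.8% are discharged by Day 15 (Protocol 7.1, Table 1), that is 510 × 0.608 = 310 patients. An assumed 0.5% to 3% risk of death between discharge and Day 28 loses 310 × 0.005 = 1.6 to 310 × 0.03 = 9.3 events.

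**Odds ratio with no treatment effect** (same *p* and *e* in both arms). With equal *s* the odds ratio is 1.00. With unequal *s*, comparing the arm with the larger share to the other:

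| *s* in the two arms | *e* | OR, *p* = 0.115 | OR, *p* = 0.17 |
|---|---|---|---|
| 10% vs 5% | 0 | 0.941 | 0.938 |
| 10% vs 5% | 2% | 0.949 | 0.943 |
| 20% vs 10% | 0 | 0.878 | 0.871 |
| 20% vs 10% | 2% | 0.895 | 0.884 |

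Example, first cell: 0.115 × 0.90 = 0.1035 and 0.115 × 0.95 = 0.10925, so the odds ratio is (0.1035/0.8965) / (0.10925/0.89075) = 0.941.

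**Scale.** With 255 per arm and *p* = 0.115, the unadjusted standard error of the log odds ratio is √[2/(255 × 0.115 × 0.885)] = 0.28. A shift to 0.941 is 0.06 on the log scale, about 0.2 standard errors. A shift to 0.878 is 0.13, about 0.5 standard errors.

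**The case against.** **The window may limit only ECMO.** Grammatically it can attach to receipt of ECMO alone, and SAP 7.5 uses a similar window and the same label for supportive-therapy data while counting death in any location. This reading is possible but less natural: one window and one label cover the whole entry, and the explicit death rule found in the days-free entries is missing. If it is what the sponsor meant, two programmers could still derive different variables, and the same sentence is needed.

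**The limit may be deliberate.** Appendix B is where composites are defined, the outcome lists hold only short names, and the all-location rule in SAP 7.5 is stated for days-free outcomes alone. Time to recovery also ignores deaths after discharge. All of this is true, and a common window for both components is a coherent choice. But for time to recovery the SAP says outright that such deaths are ignored; here it says nothing and gives no reason.

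**The illustration rests on assumptions.** This stands. The 17% is in-hospital mortality and so already excludes deaths after discharge. Read that way, the loss is 510 × 0.17 × *s*/(1 − *s*), or 4.6 at 5% and 9.6 at 10%, slightly more than shown. Nothing in the documents suggests that the arms differ in *s*, and the odds-ratio shifts are small beside sampling error.

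**No death is lost to the trial.** This also stands. Mortality, survival, the Day 29 scale and the days-free outcomes all count these deaths, and the composite is one of 14 secondary outcomes in SAP 6.2.

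**Conclusion.** The concern holds. As written, Appendix B leaves deaths after discharge out of an outcome named as running through Day 28, although the SAP collects those deaths and counts them in its other mortality-based outcomes. The composite can therefore be smaller than 28-day mortality.

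The size cannot be fixed from the documents. About 3 to 9 lost events in 510 is a plausible range if 5% to 10% of deaths follow discharge. Bias in the odds ratio needs the arms to differ in that share; with equal shares only events are lost. The problem is confined to one binary secondary outcome. The primary analysis, sample size and stopping rules are untouched. It should be corrected because the inconsistency is clear and the remedy is nearly free.

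**What to change.** In SAP Appendix B, define the composite as either of the following: death from any cause and in any location through 28 days after randomisation, taken from the hospital record and the Day 8, 15 and 29 calls as for 28-day mortality; or receipt of ECMO after randomisation during the index hospitalisation. Keep the existing rule for patients on ECMO at randomisation. The composite then cannot be smaller than 28-day mortality.

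If in-hospital death is really intended, the minimum is to put that in the outcome's name and state the reason. That removes the mismatch but still leaves available deaths uncounted.

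The cost is one sentence and one changed derivation. No new data are needed and nothing is added for patients or sites.

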For calculation of oxygen-free days, supplemental oxygen was defined as oxygen administered by nasal cannula, face mask, high-flow nasal cannula, non-invasive ventilation, or invasive ventilation. Positive airway pressure (CPAP, BiPAP) provided solely at night as treatment for sleep-disordered breathing (e.g. obstructive sleep apnea) was not considered supplemental oxygen. Oxygen-free days were calculated as the number of whole calendar days alive and not receiving supplemental oxygen between randomization and study day 29. Patients who died before Day 29 received a value of 0. If a patient survived through study day 29 and never received supplemental oxygen, the number of oxygen-free days was 28. If a patient received supplemental oxygen and survived through study day 28, the number of oxygen free-days was calculated as 28 minus the number of calendar days from the first day on which the patient received supplemental oxygen until the last day on which the patient received supplemental oxygen. Days on which the patient did not receive supplemental oxygen that occurred between days on which the patient received supplemental oxygen did not count towards the number of oxygen free days. Data on oxygen use were censored at hospital discharge and the last observed status was carried forward (“in-hospital outcome”). That is, if the patient was receiving supplement oxygen at hospital discharge, the analysis assumed they continued to receive supplemental oxygen through Study Day 29. If the patient was not receiving supplemental oxygen at hospital discharge, the analysis assumed the patient continued not to receive supplemental oxygen through Study Day 29.

Ventilator-free days to Day 28

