Ventilator-free days to day 28 was defined as the number of whole calendar days alive and breathing without invasive mechanical ventilation from 00:00 on the day of randomization through Study Day 29. Patients who died before Study Day 29 received a value of 0. If a patient survived to the first of discharge or Study Day 29 and never received invasive mechanical ventilation, the number of VFDs was 28. If a patient received invasive mechanical ventilation and survived to the first of hospital discharge or Study Day 28, the number of VFDs was calculated as 28 minus the number of calendar days from the first day on which the patient received invasive mechanical ventilation until the last day on which the patient received invasive mechanical ventilation. Days on which the patient did not receive invasive mechanical ventilation that occurred between days on which the patient received mechanical ventilation did not count towards the number of VFDs. Data on ventilation were censored at hospital discharge and the last observed status was carried forward (“in-hospital outcome”). That is, if the patient was receiving invasive mechanical ventilation at hospital discharge, the analysis assumed they continued to receive invasive mechanical ventilation through Study Day 29. If the patient was not receiving invasive mechanical ventilation at hospital discharge, the analysis assumed the patient continued not to receive invasive mechanical ventilation through Study Day 29.

Vasopressor-free days to Day 28

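### SAP Appendix B ends the free-day count on Study Day 28 in its general rule but on Study Day 29 in the outcome paragraphs, so one literal coding scores some survivors below the dead

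*SAP*

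**What the plan says.** SAP Appendix B, under Days Free of Support, opens with a rule whose scope is general: "For all outcomes related to days alive and free from a supportive therapy". The count runs "from 00:00 on the day of randomization (Study Day 1) to 23:59 on Study Day 28", and the day of randomization is included ("The day of randomization contributed to the count of" free days).

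The outcome paragraphs that follow use a different end point. Oxygen-free days are described as a count between randomization and Study Day 29. Ventilator-, vasopressor-, ICU- and hospital-free days are each described as running through Study Day 29. The oxygen, ventilator and ICU paragraphs also mix the two days, because the condition for applying their formula refers to survival to Study Day 28.

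The oxygen score for a supported survivor is "28 minus the number of calendar days from the first day on which the patient received supplemental oxygen until the last day" of oxygen. A patient discharged on oxygen is carried forward: "the analysis assumed they continued to receive supplemental oxygen through Study Day 29". The ventilator paragraph does the same ("the analysis assumed they continued to receive invasive mechanical ventilation through Study Day 29"), and so does the vasopressor paragraph. A survivor who never needed oxygen scores 28. For deaths the oxygen paragraph says "Patients who died before Day 29 received a value of 0", and the other outcomes follow the same rule. No minimum is written for supported survivors on oxygen-, ventilator-, vasopressor- or ICU-free days. Hospital-free days do have an explicit 0 for a patient in hospital through Study Day 29.

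SAP Appendix A lists all these outcomes as ordinal secondary outcomes analysed by proportional odds.

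**The concern.** Subtracting a span that may end on Day 29 from a total of 28 mixes two windows. In a proportional odds model only the order of the scores counts, so one day can matter where it changes the order relative to death. If the outcome paragraphs are coded as they stand, being alive on unbroken support becomes a category below death, and a treatment that turned deaths into survival on support would look harmful on that contrast. If the general rule is coded, the two groups tie. Two competent programmers could therefore deliver different variables from the same SAP.

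Oxygen-free days are the most exposed. A Day 29 end point can arise from an inpatient still on oxygen or, through the carry-forward rule, from anyone discharged on oxygen, and the inclusion criteria contemplate patients on chronic oxygen therapy. For vasopressors, the carry-forward would need a patient discharged while receiving them, which should be rare.

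**Working it through.** **Inputs (SAP Appendix B).** General window: Study Days 1 to 28. End point in the outcome paragraphs and of the carried-forward support: Study Day 29. Constant in the formula: 28. Score for death before Study Day 29: 0. Score for a survivor never supported: 28.

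**Which window gives the plan's own maximum of 28?** Window length = last day - first day + 1.
- Days 1 to 28: 28 - 1 + 1 = 28, which matches.
- Days 1 to 29: 29 - 1 + 1 = 29, which does not.

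**Scores for supported survivors.** Score = 28 - (last support day - first support day + 1), with support cut to the window.

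| Support | General window, Days 1-28 | Outcome paragraphs, inclusive to Day 29 | Date difference to Day 29 |
|---|---|---|---|
| Day 1 only | 27 | 27 | 28 |
| Days 3-10 | 20 | 20 | 21 |
| Days 1-28 | 0 | 0 | 1 |
| Days 2-29 | 1 | 0 | 1 |
| Days 1-29 | 28 - 28 = 0 | 28 - 29 = -1 | 28 - 28 = 0 |

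The two inclusive readings differ only for survivors on support on Day 29, and always by one day. Only those supported from Day 1 fall below 0.

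Counting by date difference avoids the -1, but it gives 28 to a patient with one day of support, the same as a patient never supported. That conflicts with a count of days not receiving support.

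**The start of the span.** The outcome formulas do not tie the first support day to randomization, and Protocol section 6.2 collects the date of first oxygen among assessments that start at hospital presentation. If oxygen began two calendar days before Day 1 (an assumption) and those days were subtracted, the span to Day 29 would be 31 days and the score 28 - 31 = -3. The general window again gives 0.

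**Effect on the odds ratio (illustration).** The documents give no proportion with unbroken oxygen. Assume 5%, 10% or 20% in the placebo group; of 510 planned patients, those shares would be about 26, 51 and 102. Assume 14% deaths on placebo and 10% on treatment, with the 4 points moved entirely to survival on unbroken oxygen and the rest of the distribution identical. Proportional odds models fitted to these expected proportions, without covariates, give:

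| Unbroken oxygen, placebo | Survivors at -1, deaths at 0 | Both at 0 | Death as lowest category |
|---|---|---|---|
| 5% | 0.977 | 1.000 | 1.02 |
| 10% | 0.971 | 1.000 | 1.03 |
| 20% | 0.959 | 1.000 | 1.04 |

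The results barely change whether the remaining patients are spread over 5, 10 or 20 levels.

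For scale, the standard error of the log odds ratio for a many-level outcome with 510 patients is about sqrt(12/510) = 0.153. The largest shift is -ln(0.959) = 0.042, and 0.042/0.153 = 0.27 standard errors.

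**The case against.** The best reply is that the general rule already settles the matter. It covers every free-day outcome, it ends at 23:59 on Study Day 28, and at most 28 support days fit inside it, so the lowest score is 0. Other text agrees: the outcome titles refer to Day 28, the maximum is 28, the outcomes are defined as numbers of whole days (which cannot be negative), and hospital-free days carry an explicit 0. Most of this stands. A reader might infer from the outcome paragraphs that the SAP ranks survivors on continuous support below the dead. The documents do not support that as the plan's settled rule, because the general window gives a tie at 0.

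The reply does not dispose of the contradiction. The general rule says which days are counted. It does not say that the span subtracted in the later formulas is cut at Day 28, and the later paragraphs restate the end point as Day 29. Those paragraphs hold the formulas, so they are likely to be the ones coded.

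It is also fair that the illustration was chosen to expose the effect, that its shares are assumed, and that the shift is small against the standard error.

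**Conclusion.** Appendix B contradicts itself on the end of the window for free-day outcomes. On one reading a survivor supported from Day 1 through Day 29 scores 0 and ties with the dead. On the other that survivor scores -1 and ranks below them, and every other survivor on support on Day 29 loses one day. The Day 28 reading is the better supported, since it alone reproduces the stated maximum of 28. A missing floor is not the root of the problem: once support is counted only within Study Days 1 to 28, a floor never binds.

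The number of patients affected cannot be obtained from the documents. Under the assumptions above, the odds ratio for oxygen-free days shifts by 0.02 to 0.04, towards apparent harm in a scenario where treatment turns deaths into survival on oxygen. No size was worked out for the other free-day outcomes. The primary outcome, the stopping guidelines and the mortality analyses do not use these scores. The point is worth correcting because the correction is cheap and removes an ordering that would be hard to defend.

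**What to change.** In SAP Appendix B, state one rule for oxygen-, ventilator-, vasopressor- and ICU-free days:

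- Death at any location before Study Day 29 scores 0, whatever else applies.
- Otherwise the value is 28 minus the span from first to last support day, counted inclusively and using only days within Study Days 1 to 28. Days before randomization and Day 29 itself are not subtracted. The minimum is then 0.

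Change the end point from Study Day 29 to Study Day 28 in the window sentences of the outcome paragraphs and in the carry-forward sentences. Adding a floor at 0 while keeping Day 29 would not be enough: a survivor supported on Days 2 to 29 would still score 0 instead of 1.

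The cost is SAP wording and about one line of derivation code. No new data are needed.

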6.3 Assessments following Hospital Discharge

6.3.1 Acute Care Follow-up

For participants discharged from the study hospital prior to the Day 8, Day 15 or Day 29 assessment, we will perform these assessments via telephone follow-up. The Day 8 call window will be Day 8 through 14. The Day 15 call window will be Day 15 through 22. The Day 29 call window will be Day 29 through 36. During these telephone calls, we will interview the patient, LAR, or facility staff to assess:

- Number and reason for missed doses of study drug (only for those discharged prior to completing study drug)
- Date of death (if applicable)
- ED visits, hospital readmissions, and use of supplemental oxygen after hospital discharge
- Non-laboratory safety outcomes after hospital discharge and adverse events
- Symptoms of acute respiratory infection
- COVID Ordinal Outcomes Scale

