SpO ₂ : FiO ₂ ≥214 and <357	2
SpO ₂ : FiO ₂ ≥89 and <214	3
SpO ₂ : FiO ₂ <89	4

When no P:F or S:F ratio is available, the respiratory SOFA score was imputed as the median observed value in the patients in the trial with non-missing values, consistent with the approach to missingness for other variables.

Definition of Secondary Outcomes

Time to Recovery

Recovery was defined as reaching category 5, 6, or 7 on the seven-category COVID Ordinal Outcome Scale. A patient could reach category 5, 6, or 7 on the seven-category COVID Ordinal Outcome Scale either by (a) being discharged from the hospital or by (b) being liberated from supplemental oxygen for the final time during the index hospitalization. Time to recovery was defined as the time between randomization and the first of either hospital discharge or liberation from supplemental

oxygen for the final time during the index hospitalization. Time to recovery was an “in-hospital outcome” and did not reflect information on receipt of supplemental oxygen, rehospitalization, or death after discharge from the index hospitalization.

For a patient who was not receiving supplemental oxygen at the time of randomization, and never received supplemental oxygen during the index hospitalization, the time to recovery was 0.0 days. For a patient who received supplemental oxygen at any time between randomization and discharge from the index hospitalization, but was not receiving supplemental oxygen at the time of discharge from the index hospitalization, the time to recovery was the time from randomization to the time of final receipt of supplemental oxygen during the index hospitalization. For a patient who was receiving supplemental oxygen at the time of discharge from the index hospitalization, the time to recovery was the time from randomization to the time of discharge from the index hospitalization. Patients who remained hospitalized and receiving supplemental oxygen 28 days after randomization were not considered to have experienced recovery. All patients who died prior to discharge from the index hospitalization were not considered to have experienced recovery. Patients who did not experience recovery were awarded a value for the outcome of time to recovery of 28.0 days.

All-location, all-cause 14-day mortality

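### Oxygen-free days assume that patients discharged on oxygen stay on it to Day 29, although the follow-up calls ask about oxygen use; the rule can rank short oxygen courses below long ones

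*SAP*

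**What the plan says.** SAP Appendix B (Oxygen-free days through Day 28) scores a surviving patient who received oxygen as "28 minus the number of calendar days from the first day on which the patient received supplemental oxygen until the last day" of receipt. Deaths are set at the bottom of the scale: "Patients who died before Day 29 received a value of 0". Oxygen data are censored at discharge and the last status is carried forward, so that "if the patient was receiving supplement oxygen at hospital discharge, the analysis assumed they continued to receive supplemental oxygen through Study Day 29".

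Three places describe where the data come from, and they do not agree:

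- Protocol 6.3.1 lists among the items assessed at the post-discharge calls "ED visits, hospital readmissions, and use of supplemental oxygen after hospital discharge".
- SAP 7.5 gives the reason for restricting free-day outcomes to the index stay: "Detailed data on receipt of invasive mechanical ventilation, vasopressors, intensive care unit admission, and hospitalization were collected during the index hospitalization, but not after discharge". Oxygen is not named there.
- SAP Appendix B (Days Free of Support) names oxygen with ventilation, vasopressors and ICU care as information gathered during the index hospitalization.

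SAP Appendix B (Time to Recovery) treats the same patients differently and dates their recovery to discharge. The rule begins "For a patient who was receiving supplemental oxygen at the time of discharge from the index hospitalization, the time to recovery was the time", and it stops the clock when the patient leaves hospital.

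**The concern.** The carry-forward rule fills the period after discharge with the longest possible oxygen course, yet the protocol plans to ask about that period. For these patients neither the discharge day nor the true stop day affects the score; only the day oxygen started does. The outcome is analysed with a proportional odds model, which uses the ranking of patients. A rule that places short oxygen courses at or near the score for death can therefore put patients in the wrong order as well as lose precision.

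Readers would also see two secondary outcomes side by side in which the same patient recovers within days and has no oxygen-free days, with nothing in the SAP to explain why.

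**Working it through.** The plan gives no worked score to reproduce, so the scoring rule is applied directly.

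**Inputs (SAP Appendix B)**

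- Let F be the first and L the last oxygen day, both counted. Oxygen-free days = 28 − (L − F + 1).
- The counting window runs "from 00:00 on the day of randomization (Study Day 1) to 23:59 on Study Day 28", that is, 28 days.
- Time before oxygen starts is credited to the patient, under the rule that begins "Days between randomization and the first receipt of the supportive therapy and days following the last day of the support therapy both counted toward".
- Discharged on oxygen and alive at Day 29: L = 28 within this window. Death before Day 29: score 0.

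**Step 1. Score of a survivor discharged on oxygen**

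28 − (28 − F + 1) = F − 1.

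| First oxygen day | Score |
|---|---|
| 1 | 0 (equal to death) |
| 2 | 1 |
| 3 | 2 |
| 5 | 4 |
| 8 | 7 |

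**Step 2. Effect on ranking**

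| | Patient A | Patient B |
|---|---|---|
| Course | Oxygen from Day 1, discharged Day 4 on oxygen, stopped Day 8 | Oxygen Days 1 to 20 in hospital, then discharged off oxygen |
| Actual oxygen days | 8 | 20 |
| Score under the SAP | 28 − 28 = 0 | 28 − 20 = 8 |
| Score from actual days | 28 − 8 = 20 | 28 − 20 = 8 |
| Time to recovery under the SAP | about 4 − 1 = 3 days | about 20 − 1 = 19 days |

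The SAP score reverses the order given by actual oxygen days.

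**Step 3. What the calls could support**

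Protocol 6.3.1 sets the call windows at Days 8 to 14, 15 to 22 and 29 to 36. Take a patient on oxygen from Day 1, with no stop date reported, and use the first call at which the patient is off oxygen as the last possible oxygen day:

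- Off at a Day 8 call made on Day 8: at least 28 − 8 = 20.
- Off at a Day 8 call made on Day 14: at least 28 − 14 = 14.
- First found off at a Day 15 call made on Day 22: at least 28 − 22 = 6.
- First found off at the Day 29 call: the bound is 28 − 28 = 0, so this call adds nothing without a stop date.

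**Step 4. End point**

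The window closes on Day 28, but the carry-forward runs through Day 29. Counting both ends literally to Day 29, a Day 1 start gives 28 − 29 = −1, below death, and a Day 2 start gives 28 − 28 = 0. Counting elapsed days to Day 29 gives 28 − (29 − F) = F − 1, as in Step 1. The text does not say which is meant.

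**Step 5. Number affected**

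The documents give no share discharged on oxygen. Protocol 7.1, Table 1 takes 60.8% discharged by Day 15 from an earlier network trial: 510 × 0.608 = 310.1. Assumed shares of these patients going home on oxygen:

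| Assumed share | Patients of 510 |
|---|---|
| 5% | 15.5 |
| 10% | 31.0 |
| 20% | 62.0 |
| 30% | 93.0 |

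These are patients subject to the carry-forward rule. Only those whose oxygen began on Day 1 tie with deaths.

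**The case against.** The strongest defence is that the SAP does give a data-source reason covering oxygen: Appendix B groups it with the in-hospital therapies, and all the organ-support free-day measures are built the same way. Protocol 6.3.1 names oxygen use but no stop date, and Protocol 6.2 collects the date and time of final oxygen receipt only up to discharge. A call-based count would mix in-hospital dates with interval data and would depend on when, and whether, the call succeeds. The rule is prespecified and applies alike to both blinded arms. For patients on chronic oxygen, whom the inclusion criteria allow, carrying oxygen forward may be accurate.

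Most of this stands as a limit on precision. It does not rescue the rule: a call that finds the patient off oxygen shows the assumption to be false, and a bound of 14 is closer to the truth than a score of 0. The Appendix B grouping conflicts with Protocol 6.3.1; it does not settle the question.

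A reader might infer more than the documents support:

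- *All patients sent home on oxygen tie with deaths.* Only those on oxygen from Day 1 do; a later start keeps the earlier free days.
- *The two secondary outcomes contradict each other.* Time to recovery is explicitly the earlier of discharge or final liberation from oxygen. It is a different construct, so the difference needs explaining and is not an error.
- *The Day 8 call always guarantees at least 20 free days.* That holds only if the call is made on Day 8 or an early enough stop date is reported.
- *The affected survivors can be set against expected deaths.* The 11.5% mortality in the planning data is a Day 15 figure from another trial, whereas this outcome scores deaths to Day 29.

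**Conclusion.** The concern holds in a limited form. The SAP assumes the maximum oxygen duration after discharge although the protocol plans to ask about it, and the resulting score can reverse the order of patients: 0 for 8 oxygen days against 8 for 20 oxygen days. The tie with death is exact for oxygen starting on Day 1, on the Day 1 to 28 window with both ends counted.

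The range of about 16 to 93 of 510 patients rests on an assumed 5% to 30% share and on another trial's discharge figure. The documents do not show whether the calls yield stop dates.

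One of the 14 secondary outcomes in SAP 6.2 is affected. The primary outcome, the stopping guidelines and the sample size are not. A reader might infer bias between arms, since discharge timing follows randomization and could respond to treatment, but nothing in the documents shows such a difference. This should be corrected, but it does not threaten the trial's main conclusion.

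**What to change.** - **Main definition.** Update oxygen status after discharge from the Day 8, 15 and 29 calls. Use the reported stop date or, if there is none, the first call at which the patient is off oxygen. Carry status forward only beyond the last successful call. Keep the current rule as a sensitivity analysis.
- **If the call data are too coarse for a day count.** Retain the current definition and add the call-based version as the sensitivity analysis, at minimum.
- **Data source.** Reconcile Protocol 6.3.1, SAP 7.5 and SAP Appendix B (Days Free of Support) on whether oxygen use is collected after discharge.
- **End point.** State whether the count closes on Study Day 28 or 29 and whether both ends are counted, so that no score can fall below 0.
- **Reporting.** Explain beside the results that time to recovery ends at discharge even for patients still on oxygen, whereas oxygen-free days follows oxygen use.

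The cost is SAP wording and some derivation code, with no new item in the call list. The downside is that call data are interval-level: a Day 1 starter found off oxygen at a Day 8 call made on Day 14 is credited with 14 free days, which may be fewer than the true number.
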